5.3.1 Dose Selection/Modification

5.3.1.1 Dose Selection

The rationale for selection of doses to be used in this trial is provided in Section 4.0 – Background and Rationale.

Details on preparation and administration of pembrolizumab (MK-3475) are provided in the Pharmacy Manual (Appendix 12.4.)

5.3.1.2 Dose Modification

Adverse events (both non-serious and serious) associated with pembrolizumab exposure may represent an immunologic etiology. These adverse events may occur shortly after the first dose or several months after the last dose of treatment. Pembrolizumab must be withheld for drug-related toxicities and severe or life-threatening AEs as per Table 3 below. See Section 5.6.1 and Events of Clinical Interest Guidance Document for supportive care guidelines, including use of corticosteroids. Table 3

Dose Modification Guidelines for Drug-Related Adverse Events

Toxicity	Hold Treatment For Grade	Timing for Restarting Treatment	Discontinue Subject
Diarrhea/Colitis	2-3	Toxicity resolves to Grade 0-1.	Toxicity does not resolve within 12 weeks of last dose or inability to reduce corticosteroid to 10 mg or less of prednisone or equivalent per day within 12 weeks.
	4	Permanently discontinue	Permanently discontinue
AST, ALT, or Increased Bilirubin	2	Toxicity resolves to Grade 0-1	Toxicity does not resolve within 12 weeks of last dose.
	3-4	Permanently discontinue (see exception below) ¹	Permanently discontinue
Type 1 diabetes mellitus (if new onset) or Hyperglycemia	T1DM or 3-4	Hold pembrolizumab for new onset Type 1 diabetes mellitus or Grade 3-4 hyperglycemia associated with evidence of beta cell failure.	Resume pembrolizumab when patients are clinically and metabolically stable.
Hypophysitis	2-3	Toxicity resolves to Grade 0-1	Toxicity does not resolve within 12 weeks of last dose or inability to reduce corticosteroid to 10 mg or less of prednisone or equivalent per day within 12 weeks.
	4	Permanently discontinue	Permanently discontinue
Hyperthyroidism	3	Toxicity resolves to Grade 0-1	Toxicity does not resolve within 12 weeks of last dose or inability to reduce corticosteroid to 10 mg or less of prednisone or equivalent per day within 12 weeks.
	4	Permanently discontinue	Permanently discontinue
Hypothyroidism	2-4	Therapy with pembrolizumab can be continued while treatment for the thyroid disorder is instituted	Therapy with pembrolizumab can be continued while treatment for the thyroid disorder is instituted.
Infusion Reaction	3-4	Permanently discontinue	Permanently discontinue
Pneumonitis	2	Toxicity resolves to Grade 0-1	Toxicity does not resolve within 12 weeks of last dose or inability to reduce corticosteroid to 10 mg or less of prednisone or equivalent per day within 12 weeks.
	3-4	Permanently discontinue	Permanently discontinue
Renal Failure or Nephritis	2	Toxicity resolves to Grade 0-1	Toxicity does not resolve within 12 weeks of last dose or inability to reduce corticosteroid to 10 mg or less of prednisone or equivalent per day within 12 weeks.
	3-4	Permanently discontinue	Permanently discontinue
All Other Drug-Related Toxicity ²	3 or Severe	Toxicity resolves to Grade 0-1	Toxicity does not resolve within 12 weeks of last dose or inability to reduce corticosteroid to 10 mg or less of prednisone or equivalent per day within 12 weeks.
	4	Permanently discontinue	Permanently discontinue

Note: Permanently discontinue for any severe or Grade 3 (Grade 2 for [pneumonitis]) drug-related AE that recurs or any life-threatening event.

¹ For patients with liver metastasis who begin treatment with Grade 2 AST or ALT, if AST or ALT increases by greater than or equal to 50% relative to baseline and lasts for at least 1 week then patients should be discontinued.

Toxicity	Hold Treatment For Grade	Timing for Restarting Treatment	Discontinue Subject
² Patients with intolerable or persistent Grade 2 drug-related AE may hold study medication at physician discretion. Permanently discontinue study drug for persistent Grade 2 adverse reactions for which treatment with study drug has been held, that do not recover to Grade 0-1 within 12 weeks of the last dose.			

Dosing interruptions are permitted in the case of medical / surgical events or logistical reasons not related to study therapy (e.g., elective surgery, unrelated medical events, patient vacation, and/or holidays). Subjects should be placed back on study therapy within 3 weeks of the scheduled interruption, unless otherwise discussed with the Sponsor. The reason for interruption should be documented in the patient's study record.

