5.0 METHODOLOGY

5.1 Entry Criteria

5.1.1 Diagnosis/Condition for Entry into the Trial

Patients who are 18 years or older with 1) stage IV metastatic triple negative breast cancer (triple negative is defined as ER and PgR status is <1% of tumor cell nuclei are immunoreactive for ER or PgR, and HER2 status is FISH negative or IHC 0 or 1+) or 2) Stage IV HR+ HER2- (HR+) breast cancer (defined as ER or PgR $\geq 1\%$ of tumor cell nuclei are immunoreactive for ER or PgR and HER2 status is FISH negative or ICH 0 or 1+).

Subject Inclusion Criteria

In order to be eligible for participation in this trial, the subject must:

1. Be willing and able to provide written informed consent/assent for the trial.
2. Be ≥ 18 years of age on day of signing informed consent.
3. Have measurable disease based on RECIST 1.1.
4. Be willing to provide tissue from a newly obtained core or excisional biopsy of a tumor lesion. *Newly-obtained is defined as a specimen obtained up to 6 weeks (42 days) prior to initiation of treatment on Day 1. Subjects for whom newly-obtained samples cannot be provided (e.g. inaccessible or subject safety concern) may submit an archived specimen only upon agreement from the Sponsor.*
5. Have a performance status of 0 or 1 on the ECOG Performance Scale.
6. Demonstrate adequate organ function as defined in Table 1, all screening labs should be performed within 7 days of treatment initiation.

Table 1 Adequate Organ Function Laboratory Values

System	Laboratory Value
Hematological	
Absolute neutrophil count (ANC)	$\geq 1,500$ /mcL
Platelets	$\geq 100,000$ / mcL
Hemoglobin	≥ 9 g/dL or ≥ 5.6 mmol/L without transfusion or EPO dependency (within 7 days of assessment)
Renal	
Serum creatinine OR	≤ 1.5 X upper limit of normal (ULN) OR

Measured or calculated ^a creatinine clearance (GFR can also be used in place of creatinine or CrCl)	≥ 60 mL/min for subject with creatinine levels $> 1.5 \times$ institutional ULN
Cardiac	
Left ventricular ejection fraction by MUGA or Echocardiogram [#]	$\geq 55\%$; \geq upper limit of institutional normal
Hepatic	
Serum total bilirubin	$\leq 1.5 \times$ ULN OR Direct bilirubin \leq ULN for subjects with total bilirubin levels > 1.5 ULN
AST (SGOT) and ALT (SGPT)	$\leq 2.5 \times$ ULN OR $\leq 5 \times$ ULN for subjects with liver metastases
Albumin	> 2.5 mg/dL
Coagulation	

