 - Treat with an initial dose of IV corticosteroid followed by oral corticosteroids. When symptoms improve to Grade 1 or less, steroid taper should be started and continued over no less than 4 weeks. Replacement of appropriate hormones may be required as the steroid dose is tapered.
- **Hepatic:**
 - For **Grade 2** events, monitor liver function tests more frequently until returned to baseline values (consider weekly).
 - Treat with IV or oral corticosteroids
 - For **Grade 3-4** events, treat with intravenous corticosteroids for 24 to 48 hours.
 - When symptoms improve to Grade 1 or less, a steroid taper should be started and continued over no less than 4 weeks.

- **Renal Failure or Nephritis:**
 - For **Grade 2** events, treat with corticosteroids.
 - For **Grade 3-4** events, treat with systemic corticosteroids.
 - When symptoms improve to Grade 1 or less, steroid taper should be started and continued over no less than 4 weeks.
- **Management of Infusion Reactions:** Signs and symptoms usually develop during or shortly after drug infusion and generally resolve completely within 24 hours of completion of infusion.

Table

Table 4 below shows treatment guidelines for subjects who experience an infusion reaction associated with administration of pembrolizumab (MK-3475).

Table 4 Infusion Reaction Treatment Guidelines

NCI CTCAE Grade	Treatment	Premedication at subsequent dosing
Grade 1 Mild reaction; infusion interruption not indicated; intervention not indicated	Increase monitoring of vital signs as medically indicated until the subject is deemed medically stable in the opinion of the investigator.	None

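### Table 3's Grade 2 AST/ALT restart rule is not reconciled with footnote 1 or section 5.7.1 for liver-metastasis patients who begin treatment at Grade 2

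*Combined protocol and SAP*

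**What the plan says.** Four places in the protocol bear on these patients.

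- **Entry (section 5.1.1, Table 1).** AST and ALT may be up to 2.5 x ULN, or up to 5 x "ULN for subjects with liver metastases".
- **Dose modification, Grade 2 row (section 5.3.1.2, Table 3).** For Grade 2 AST, ALT or bilirubin, pembrolizumab is held. The restart condition is "Toxicity resolves to Grade 0-1". The discontinuation condition is "Toxicity does not resolve within 12 weeks of last dose". The row has no footnote mark and no baseline alternative.
- **Dose modification, Grade 3-4 row and footnote 1 (same table).** The row reads "Permanently discontinue (see exception below"), and the exception is footnote 1. Its opening names the group: "For patients with liver metastasis who begin treatment with Grade 2 AST or ALT, if AST or ALT increases". The threshold that follows is a rise from the starting value of at least half, sustained for a week or longer, at which point treatment is to stop.
- **Supportive care (section 5.7.1, Hepatic).** For Grade 2 events the instruction is to "monitor liver function tests more frequently until returned to baseline values".

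Table 3 is limited in scope: "Pembrolizumab must be withheld for drug-related toxicities and severe or life-threatening AEs as per Table 3 below".

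**The concern.** The protocol knowingly admits patients whose transaminases are already Grade 2, and it uses two yardsticks for them. Footnote 1 and section 5.7.1 look to the patient's own baseline. The Grade 2 row looks to absolute grade, at a level these patients did not have when they started. If such a patient is held, getting back to where she began is not enough to restart.

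The omission does not look deliberate. Exclusion criteria 8 and 9 (section 5.1.2) accept either Grade 1 or baseline as recovery from earlier toxicity; the Grade 2 row keeps only the first.

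For the analysis, two investigators could handle the same patient differently and both cite the protocol. Time to treatment failure, a secondary endpoint, would then depend on which line was followed. Discontinued patients are not replaced (section 5.10), and all treated Cohort 1 patients count for efficacy (section 8.2.1), so a patient taken off pembrolizumab this way stays in the response-rate denominator. In the lead-in, section 8.1.2 counts a delay of more than 2 weeks for a treatment-related event as a DLT. A hold that waits for Grade 0-1 could therefore be scored a DLT although the values had returned to baseline.

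**Working it through.** No figure in the plan depends on this rule, so the check is mainly a trace through the table.

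**Inputs.** From the documents: entry limit 5 x ULN with liver metastases; Grade 2 row restart at Grade 0-1 and limit of 12 weeks from last dose; footnote 1 threshold of a 50% rise lasting 1 week. Assumed: the documents adopt CTCAE 4.0 (section 12.2) but do not print its AST/ALT cut-offs. I take Grade 2 as running from L to U, with L between 2.5 and 3 x ULN and U = 5 x ULN. The conflict itself does not need these values, because footnote 1 says that patients may begin at Grade 2. They only show its size.

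**Formulas**, for a baseline of B x ULN:
- Level at which footnote 1 would apply: 1.5 x B
- Rise needed to pass Grade 2: U/B - 1
- Fall below baseline needed to reach Grade 0-1: 1 - L/B

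| Baseline (x ULN) | Footnote 1 level (x ULN) | Rise that reaches the top of Grade 2 | Fall below baseline needed to restart (L = 3 to L = 2.5) |
|---|---|---|---|
| 3.5 | 5.25 | 43% | 14% to 29% |
| 4.0 | 6.00 | 25% | 25% to 38% |
| 4.5 | 6.75 | 11% | 33% to 44% |
| 5.0 | 7.50 | 0% | 40% to 50% |

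**Two patients, both with baseline 4 x ULN and a drug-related rise.**
1. A rise of 20% gives 4 x 1.2 = 4.8 x ULN, still Grade 2. The Grade 2 row applies: hold. A return to 4.0 does not meet the restart condition; she must fall to between 2.5 and 3.0 x ULN. If she does not, the 12-week limit is reached.
2. A rise of 40% gives 4 x 1.4 = 5.6 x ULN, which is Grade 3 but below 6.0. Footnote 1 lifts the permanent discontinuation. The table does not say what hold or restart rule then applies.

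On a literal reading the smaller rise meets the stricter condition. The second case can arise for any baseline above 5/1.5 = 3.33 x ULN.

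**Illustration for Cohort 1.** Exact enumeration of the section 8.2.1 rule (continue with at least 4 responses in 22, success with at least 9 in 36) gives a type I error of 7.7% at 15%, within the stated 10%, and power of 90.0% at 34%, as stated. Suppose m of 36 patients lose pembrolizumab this way and respond at rate q. The overall rate is 0.34 x (1 - m/36) + q x m/36.

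| m | q = 0.15: rate, power | q = 0: rate, power |
|---|---|---|
| 2 | 0.329, 87.6% | 0.321, 85.3% |
| 4 | 0.319, 84.7% | 0.302, 79.2% |

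Both m and q are assumptions; nothing in the documents supports a value for either.

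**The case against.** The strongest reply is that no two lines give opposite orders. Footnote 1 says when these patients should be discontinued; it is silent on holding and restarting, and it is marked as an exception to the Grade 3-4 row only. A hold rule and a separate stopping rule can both apply. That stands: this is an unreconciled case, not a direct contradiction.

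A reader might also infer that any rise inside the 50% tolerance ends treatment. The documents do not support that, for four reasons.
- Table 3 covers drug-related events, and section 7.2 counts worsening of a preexisting condition as an adverse event only if clinically significant. A stable Grade 2 baseline, or a small rise not so judged, does not clearly trigger the row.
- The row orders a hold. Discontinuation follows only if the toxicity is unresolved at 12 weeks, and values can fall below baseline, for instance if liver metastases respond.
- Section 7.1.1.8 calls for consultation with the sponsor when an interruption exceeds 12 weeks.
- A rise under 50% that reaches Grade 3 is expressly excepted from permanent discontinuation.

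It can be said, too, that the discontinuation column does not repeat Grade 0-1, so resolution might mean return to baseline. This is weak: the adjacent cell of the same row defines resolution as Grade 0-1, and footnote 2 measures its own 12-week limit the same way. The ECI guidance document, which section 5.3.1.2 cites, may say more, but its text is not available here.

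The power figures are open to fair attack. Affected patients need liver metastases, a Grade 2 baseline, a drug-related rise and 12 weeks without resolution. They will have received pembrolizumab, and the flow chart places the first on-treatment scan before 12 weeks could pass, so q = 0 is implausible. Keeping discontinued patients in the denominator is ordinary practice.

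**Conclusion.** The point holds as a gap in wording. For liver-metastasis patients who begin at Grade 2, the Grade 2 AST/ALT row is not reconciled with footnote 1 or with section 5.7.1. Read literally, a patient held for a drug-related rise within Grade 2 who returns to baseline cannot restart and may be discontinued at 12 weeks, while a larger rise to Grade 3 of under 50% is excepted from permanent discontinuation.

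The conflict rests on the text alone; the size of the fall needed to restart rests on the assumed grade cut-offs. The number affected is unknown and probably small, so the power figures illustrate a direction and do not estimate a loss. They do not show a threat to the primary analysis.

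A reader might extend the point to bilirubin, since Table 1 admits some patients above 1.5 x ULN. That needs a grade boundary that the documents do not print, and bilirubin has no baseline-relative rule with which the row could conflict. I do not make that claim.

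**What to change.** Reconcile the Grade 2 hepatic row of Table 3, footnote 1, the Table 1 AST/ALT limit for liver metastases and section 5.7.1. For patients who begin at Grade 2, one consistent rule should cover hold, restart and the 12-week limit, and should say whether each is judged against baseline or absolute grade. State which rows footnote 1 covers, and what applies to a patient whom it excepts from permanent discontinuation. Which rule is right is for the sponsor's clinicians.

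The cost is an edit to one table row, its footnote and one line of section 5.7.1. It needs no extra tests, visits or patients.

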5.3.2 Timing of Dose Administration

Trial treatment should be administered on Day 1 of each cycle after all procedures/assessments have been completed as detailed on the Trial Flow Chart (Section 6.0). Trial treatment may be administered up to 3 days before or after the scheduled Day 1 of each cycle due to administrative reasons.

All trial treatments will be administered on an outpatient basis.

Pembrolizumab 200 mg will be administered as a 30 minute IV infusion every 3 weeks. Sites should make every effort to target infusion timing to be as close to 30 minutes as possible. However, given the variability of infusion pumps from site to site, a window of -5 minutes and +10 minutes is permitted (i.e., infusion time is 30 minutes: -5 min/+10 min).

Follow the package insert for the preparation of the pembrolizumab infusion fluid and administration of infusion solution.

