6.0 TRIAL FLOW CHART

6.1 Study Flow Chart

Trial Period:	Screening Phase		Treatment Cycles								End of Treatment	Post-Treatment		
	Pre-screening (Visit 1)	Main Study Screening (Visit 2)	1	2	3	4	To be repeated beyond 8 cycles					Safety Follow-up	Follow Up Visits	Survival Follow-Up
Treatment Cycle/Title:							5	6	7	8				
Scheduling Window (Days):		-28 to -1		± 3	± 3	± 3	± 3	± 3	± 3	± 3	At time of Discont.	30 days post Discont.	Every 8 weeks post Discont.	Every 12 weeks
Administrative Procedures														
Pre-screening Consent	X													
Informed Consent		X												
Inclusion/Exclusion Criteria		X												
Demographics and Medical History		X												
Prior and Concomitant Medication Review		X	X	X	X	X	X	X	X	X		X		
Trial Treatment Administration			X	X	X	X	X	X	X	X				
Post-study anticancer therapy status													X	X
Survival Status														X
Clinical Procedures/Assessments														
Review Adverse Events		X	X	X	X	X	X	X	X	X		X		
Full Physical Examination		X												
Directed Physical Examination			X	X	X	X	X	X	X	X				
Vital Signs and Weight		X	X	X	X	X	X	X	X	X				
ECOG Performance Status		X	X	X	X	X	X	X	X	X				
Laboratory Procedures/Assessments: analysis performed by LOCAL laboratory														
Pregnancy Test – Urine or Serum β-HCG		X												
PT/INR and aPTT		X												
CBC with Differential		X	X	X	X	X	X	X	X	X		X		

Trial Period:	Screening Phase		Treatment Cycles								End of Treatment	Post-Treatment			
	Treatment Cycle/Title:	Pre-screening (Visit 1)	Main Study Screening (Visit 2)	1	2	3	4	To be repeated beyond 8 cycles				Discont.	Safety Follow-up	Follow Up Visits	Survival Follow-Up
Scheduling Window (Days):				-28 to -1	± 3	± 3	± 3	± 3	± 3	± 3	± 3				
Comprehensive Serum Chemistry Panel		X	X	X	X	X	X	X	X	X	X	X	X		
Urinalysis		X		X		X		X		X			X		
T3, FT4 and TSH		X		X		X		X		X			X		
Efficacy Measurements															
Tumor Imaging with CT (chest, abdomen, pelvis, bone scan, other modalities as deemed appropriate clinically)		X			X			X			X				
Cardiac evaluation: Echo, or MUGA and ECG for triple negative and MUGA or ECHO for the HR+ cohort		X								X@					
Tumor Biopsies/Archival Tissue Collection/Correlative Studies Blood															
Archival or Newly Obtained Tissue Collection		X		X#							X				
Correlative Studies Blood Collection##		X		X							X				
#optional ## if pts agree ask for weeks 4,6,8,10, 20,30															

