7.1.2.7 Tumor Tissue Collection and Correlative Studies Blood Sampling

Laboratory Procedures/Assessments

Details regarding specific laboratory procedures/assessments to be performed in this trial are provided below Laboratory Safety Evaluations (Hematology, Chemistry and Urinalysis)

Laboratory tests for hematology, chemistry, urinalysis, and others are specified in Table 5.

Table 5 Laboratory Tests

Hematology	Chemistry	Urinalysis	Other
Hematocrit	Albumin	Blood	Serum β -human chorionic gonadotropin†
Hemoglobin	Alkaline phosphatase	Glucose	(β -hCG)†
Platelet count	Alanine aminotransferase (ALT)	Protein	PT (INR)
WBC (total and differential)	Aspartate aminotransferase (AST)	Specific gravity	aPTT
Red Blood Cell Count	Lactate dehydrogenase (LDH)	Microscopic exam (If abnormal)	Total triiodothyronine (T3)
Absolute Neutrophil Count	Carbon Dioxide ‡	results are noted	Free tyroxine (T4)
Absolute Lymphocyte Count	(CO_2 or bicarbonate)	Urine pregnancy test †	Thyroid stimulating hormone (TSH)
	Uric Acid		PK
	Calcium		
	Chloride		Blood for correlative studies
	Glucose		
	Phosphorus		
	Potassium		
	Sodium		
	Magnesium		
	Total Bilirubin		
	Direct Bilirubin		
	Total protein		
	Blood Urea Nitrogen		

† Perform on women of childbearing potential only. If urine pregnancy results cannot be confirmed as negative, a serum pregnancy test will be required.

‡ If considered standard of care in your region.

Laboratory tests for screening or entry into the Second Course Phase should be performed within 7 days prior to the first dose of treatment. After Cycle 1, pre-dose laboratory procedures can be conducted up to 72 hours prior to dosing. Results must be reviewed by the investigator or qualified designee and found to be acceptable prior to each dose of trial treatment.

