Subjects should be assessed for possible ECIs prior to each dose. Lab results should be evaluated and subjects should be asked for signs and symptoms suggestive of an immune-related event. Subjects who develop an ECI thought to be immune-related should have additional testing to rule out other etiologic causes. If lab results or symptoms indicate a possible immune-related ECI, then additional testing should be performed to rule out other etiologic causes. If no other cause is found, then it is assumed to be immune-related.

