	Is an overdose (whether accidental or intentional). Any adverse event associated with an overdose is considered a serious adverse event. An overdose that is not associated with an adverse event is considered a non-serious event of clinical interest and must be reported within 24 hours.	
	Other important medical events that may not result in death, not be life threatening, or not require hospitalization may be considered a serious adverse event when, based upon appropriate medical judgment, the event may jeopardize the subject and may require medical or surgical intervention to prevent one of the outcomes listed previously (designated above by a †).	
Duration	Record the start and stop dates of the adverse event. If less than 1 day, indicate the appropriate length of time and units	
Action taken	Did the adverse event cause the Merck product to be discontinued?	
Relationship to test drug	Did the Merck product cause the adverse event? The determination of the likelihood that the Merck product caused the adverse event will be provided by an investigator who is a qualified physician. The investigator's signed/dated initials on the source document or worksheet that supports the causality noted on the AE form, ensures that a medically qualified assessment of causality was done. This initialed document must be retained for the required regulatory time frame. The criteria below are intended as reference guidelines to assist the investigator in assessing the likelihood of a relationship between the test drug and the adverse event based upon the available information.	
	The following components are to be used to assess the relationship between the Merck product and the AE; the greater the correlation with the components and their respective elements (in number and/or intensity), the more likely the Merck product caused the adverse event (AE):	
	Exposure	Is there evidence that the subject was actually exposed to the Merck product such as: reliable history, acceptable compliance assessment (pill count, diary, etc.), expected pharmacologic effect, or measurement of drug/metabolite in bodily specimen?
	Time Course	Did the AE follow in a reasonable temporal sequence from administration of the Merck product? Is the time of onset of the AE compatible with a drug-induced effect (applies to trials with investigational medicinal product)?

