8.1.2 Definitions of DLTs

DLTs for both cohorts are defined as:

Hematologic Toxicities:

- Any Grade 4 thrombocytopenia or neutropenia lasting >7 days

Nonhematologic Toxicities:

- Episcleritis, uveitis, or iritis of Grade 2 or higher

- Any Grade 4 toxicity

- Any Grade 3 toxicity EXCLUDING:

- Nausea, vomiting, or diarrhea controlled by medical intervention within 72 hours
 - Grade 3 rash in the absence of desquamation, no mucosal involvement, does not require steroids, and resolves to Grade 1 by the next scheduled dose of pembrolizumab.
 - Rapidly reversible electrolyte abnormalities (within 72 hrs.).
 - Transient Grade 3 AST or ALT elevation, defined as no more than 3 days with or without steroid use

- Discontinuation or delay of more than 2 weeks of any study drug due to treatment-related AE will be considered as a DLT

Toxicity will be graded according to the NCI CTCAE version 4.0. To be evaluable for toxicity, a patient must receive at least one complete course of treatment and be observed for at least 21 days after the start of the first course or have experienced a DLT. All patients who receive any amount of drug will be considered evaluable for toxicity.

8.1.3 3-at-risk—Rules of Level Assignment

3-at-risk -- Rules for Dose Level Assignment

# Patients on Current Level			Action
DLT	EVAL	EVAL+At Risk	
0	0	1-2	Accrue next patient at this level*
0	0	3	Hold accrual
0	1	1-3	Accrue next patient at this level
0	1	4	Hold accrual
0	2	2-4	Accrue next patient at this level
0	2	5	Hold accrual
0	3	3-5	Accrue next patient at the next higher level*
1	1	1-2	Accrue next patient at this level
1	1	3	Hold Accrual
1	2	2	Accrue next patient at this level
1	2	3-4	Hold accrual
1	3-5	3-5	Accrue next patient at this level
1	3-5	6	Hold accrual
1	6	6	Accrue next patient at the next higher level*
2**	any	Any	Accrue next patient at the next lower level to a maximum of 6

*If in dose-escalation portion. If higher dose level already closed, the next lower dose will accrue to a total of 6 patients, with 2 or higher DLTs requiring further dose de-escalation. If there is no next higher dose, the next patient will be accrued to the current level.
 
**Patients treated on a higher dose during cycle 1 will have their treatment modified to the dose below the dose level with 2 DLTs.
			

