Note: “DLT” – a patient with a documented first-cycle DLT; “PASS” – a patient without a first-cycle DLT fully evaluable for toxicity for the purpose of dose escalations; “EVAL” – a patient who is either DLT or PASS; “Inevaluable” – a patient who is off treatment without being DLT or PASS; “At Risk” – a patient who is on study in the first cycle and not yet DLT, PASS, or Inevaluable

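### The minus-3-day dosing window has no safety lead-in exception, so cycle 2 can be given on Day 19, before the 21-day DLT observation is complete

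*Combined protocol and SAP*

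**What the plan says.** Section 5.3.2 (Timing of Dose Administration) sets the window: "Trial treatment may be administered up to 3 days before or after the scheduled Day 1 of each cycle due to administrative reasons". The scheduling-window row of the flow chart in 6.1 gives ±3 days at cycle 2 and has no lead-in footnote. Table 2 in 5.3 sets 3-week cycles.

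Section 8.1.2 says that, to be evaluable for toxicity, a patient must receive one complete course and "be observed for at least 21 days after the start of the first course or have experienced a DLT". The note under the level-assignment table in 8.1.3 defines PASS as "a patient without a first-cycle DLT fully evaluable for toxicity for the purpose of dose escalations".

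The remaining lead-in text (5.3.3, 8.1.1.1 and the 8.1.3 table) caps the number of patients at risk at three per treatment and sets the next level. The ** footnote to the table adds that, once a level has 2 DLTs, patients treated at that higher dose in cycle 1 are moved to the dose below. None of these sections suspends the early window or says when a lead-in patient may receive cycle 2.

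**The concern.** The lead-in judges one cycle of a combination that 4.1.5 describes as not previously tested, and its decisions rest on 3 to 6 patients per level. The protocol fixes 21 days as the time needed to see first-cycle toxicity, yet it lets the second dose fall inside those days.

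Two things are at stake, both confined to events that first appear on Days 19 to 21.

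- **Patient safety.** The patient has already had a second full dose. Had dosing waited until Day 22, the event could have led to a hold. At level 2 of Cohort 1, if the event brought the level to 2 DLTs, the ** footnote would have reduced that patient's dose, and that of any other level 2 patient about to be re-dosed. A dose already given cannot be reduced.
- **Attribution.** If dose 2 contributes to the event, a toxicity of two doses is counted as a first-cycle DLT. The error is then toward caution: the level looks more toxic than one cycle of it is.

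The point concerns mainly Cohort 1, where doxorubicin and pembrolizumab both move forward. In Cohort 2 the aromatase inhibitor is taken daily, so only pembrolizumab moves.

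**Working it through.** The plan gives no figure of its own here.

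**Dates.** Inputs are the 3-week cycle (Table 2), the ±3-day window (5.3.2 and 6.1) and the 21-day minimum (8.1.2). The first dose is on Day 1, so cycle 2 is scheduled on Day 1 + 21 = Day 22.

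| Cycle 2 dose | Days since first dose | Short of 21 days by |
|---|---|---|
| Day 19 (−3) | 18 | 3 |
| Day 20 (−2) | 19 | 2 |
| Day 21 (−1) | 20 | 1 |
| Day 22 (0) | 21 | 0 |
| Day 25 (+3) | 24 | 0 |

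Reading the requirement as Days 1 to 21 inclusive does not help, because Days 19, 20 and 21 are still unobserved at a Day 19 dose.

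**Age of laboratory results.** After cycle 1, 7.1.2.7 accepts pre-dose results up to 72 hours old. A Day 19 dose may therefore rest on Day 16 samples (19 − 3), and a Day 22 dose on Day 19 samples (22 − 3). Moving the dose to Day 22 alone would still let a laboratory DLT arising on Days 20 or 21 go unseen before dosing.

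**Size.** The documents give no DLT rate, no DLT timing and no frequency of early dosing. Assume a true 21-day DLT rate p and a constant hazard that dose 2 does not change. For a patient with no DLT through Day 18 who is dosed on Day 19, the chance that a first DLT appears on Days 19 to 21 is

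1 − (1 − p)^(3/21).

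| p | Chance |
|---|---|
| 10% | 1.5% |
| 20% | 3.1% |
| 30% | 5.0% |
| 40% | 7.0% |

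At p = 30%, a dose 2 days early gives 1 − 0.7^(2/21) = 3.3%, and 1 day early gives 1 − 0.7^(1/21) = 1.7%. From Day 22 on, the chance of a first DLT after dose 2 but within the 21 days is zero by construction.

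**Decision rule.** For the Cohort 2 lead-in rule of at most 1 DLT in 6 patients, the binomial probability of success is 65.5%, 42.0% and 23.3% at p = 20%, 30% and 40%. Under the same assumption, early dosing does not change these values, because events on Days 19 to 21 are still counted. If dose 2 raises the hazard, they would be lower.

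**The case against.** The other side has a good case, and much of it stands.

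- **Known toxicity is caught.** Section 5.3.1.2 says "Pembrolizumab must be withheld for drug-related toxicities and severe or life-threatening AEs as per Table 3 below"; 7.1.2.7 says of laboratory results "Results must be reviewed by the investigator or qualified designee and found to be acceptable prior to each dose of trial treatment"; and 7.2.13.2 says "Subjects should be assessed for possible ECIs prior to each dose". This is right, but these checks act only on what is visible at dosing. They cannot act on an event that begins afterwards, and early dosing brings forward the only scheduled safety review near the end of the observation period.
- **No event is lost.** A reader might infer that a toxicity on Days 19 to 21 drops out of the first-cycle count. The documents do not support that. The 21 days run from the start of the first course whatever the date of dose 2, and Table 6 in 7.2.14 tells the investigator to "Record the start and stop dates of the adverse event".
- **PASS is not a gate to cycle 2.** A reader might infer that early dosing breaches a required sequence. It does not: PASS governs escalation and accrual, and no section makes it a condition of a patient's own next dose. After an early dose, observation can run to 21 days and PASS can then be assigned.
- **The two harms rest on different assumptions.** If dose 2 leaves the hazard unchanged, every such event would have occurred anyway and the count is sound; only the dose that could have been held remains. Contamination of the count needs dose 2 to raise the hazard, and nothing in the documents allows that effect to be sized.
- **Exposure is the planned exposure, three days sooner.** Section 4.1.4 reports no dose-limiting toxicities with single-agent pembrolizumab every 2 weeks at up to 10 mg/kg. What is new in Cohort 1 is mainly a doxorubicin dose at 18 rather than 21 days.
- **Early dosing is an exception.** It is allowed only for administrative reasons, at one institution, with few patients at risk at a time. It may never happen in the lead-in.

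**Conclusion.** The gap is real and small. As written, a lead-in patient can be re-dosed up to 3 days before the DLT observation is complete, and no lead-in provision prevents it. The date arithmetic is certain.

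The 1.5% to 7.0% applies only to a patient actually dosed on Day 19 and rests on assumed DLT rates and a constant hazard. It understates the chance if dose 2 raises the hazard and overstates it if toxicity tends to appear early in the cycle. It should not be compounded across several patients as though all were dosed at the edge of the window.

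A reader might go further and infer that the lead-in decisions or the efficacy results are unreliable. The documents do not support that: the scoring rules stand, any contamination is toward caution, and the phase II sample sizes and response rules do not depend on this window. This is an inexpensive improvement to safety and attribution, not a flaw that invalidates the design.

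**What to change.** Add one sentence to 5.3.2 and one footnote to the flow chart in 6.1, for safety lead-in patients only:

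- Cycle 2 may not be given before Day 22 (window 0 to +3 days, that is, Days 22 to 25).
- Toxicity through Day 21 is reviewed at that visit before dosing.
- Pre-dose laboratory samples for that visit are drawn no earlier than Day 21, in place of the 72-hour allowance in 7.1.2.7 where that would accept older samples. For a Day 25 dose the 72-hour limit is the tighter one (25 − 3 = Day 22) and can stay.

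Leave the DLT definition in 8.1.2 unchanged, so that criteria that settle later still count: a treatment-related delay of more than 2 weeks, and Grade 4 thrombocytopenia or neutropenia lasting more than 7 days.

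The cost is slightly less scheduling flexibility at one visit, for the few patients in the lead-in.
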